7.1.4 Behavioral Risks

The results from the Proof-of Principle, Feasibility and Pilot Studies did not detect any adverse behavioral effects of Aspiration Therapy. Nonetheless, there are two potential behavioral concerns with the use of this therapy: (i) excessive use of the aspiration therapy that causes excessive weight loss and nutritional/metabolic abnormalities, or (ii) adverse eating behaviors (increased food intake) because of the ability to aspirate after meals.

However, both of these potential concerns are very unlikely to occur, and we have established important safeguards to prevent and identify them (discussed below).

Overuse of Aspiration Therapy

In the studies to date, there has been no indication of excessive use of Aspiration Therapy in any subject assessed by: (i) **Connector** usage, documented by the **Counter** (on the Connector), which was consistent with normal use and (ii) rate of weight loss - no subject lost weight at a faster rate than expected.

Although there is always the possibility that a subject will attempt to over-use the therapy, this is unlikely to occur because the **Counter** prevents a subject from using the Connector more than 115 aspiration cycles, at which the point the subject would need to return to his physician to obtain a new Connector. The Connector (when it is connected to the Skin-Port opens) the normally-closed valve in the Skin-Port to allow aspiration. The Skin-Port valve automatically closes when the Connector is removed; the Connector is bulky and would protrude through clothing so that subjects want to remove it post-aspiration. There has been no evidence of subjects in the trials tampering with the Connector.

In the current study, subjects are asked to bring their connector to each study visit so the counts may be documented. If the study team suspects a subject has attempted to override the counting mechanism, that subject will be dropped from the study and his/her data will not be included in efficacy analyses, but will be included in analysis of safety data.

Abnormal Eating Behavior

The results from the Feasibility and Pilot Studies did not detect any adverse effects of aspiration therapy on eating behavior or any evidence that subjects increased the volume of food intake or frequency of eating because of the ability to aspirate. In these studies, eating behavior was evaluated by using a series of validated questionnaires and a structured psychological interview. In fact, there was evidence of improvement in eating behavioral traits (improved restraint, less disinhibition, more control over food intake, and decreased hunger).

7. 1.5 Risks Associated with Concomitant Drug Therapy

The drugs prescribed as part of the protocol include (i) prophylactic antibiotics to prevent infection after A-tube insertion, and ii) pain medication after A-Tube placements (at the physician's discretion). In addition, a multivitamin and mineral supplement will be taken throughout the duration of the study. The side effects are described below. Serious side effects of these medications are unlikely to occur because they will be given for a short period of time.

Keflex (an antibiotic given to those in the Aspiration Therapy group before and after A-Tube placement) in rare cases may cause diarrhea.

Clindamycin (an antibiotic given to subjects in the Aspiration Therapy group who are allergic to penicillin before and after A-Tube placement) may cause diarrhea, and in rare case may cause

rash, nausea, vomiting, low blood pressure, itching, inflammation of the colon.

Ultram (given to the Aspiration Therapy group for possible pain after A-Tube placement) in rare cases can cause dizziness, headache, sleepiness, restlessness, nausea, diarrhea, constipation, vomiting, stomach ache, weakness, sweating.

Silver nitrate sticks (skin product used, if necessary, to treat scar tissue around the A-Tube) may cause burning and skin irritation, and in rare case may cause skin staining.

Other medications may be prescribed at the discretion of the investigator (e.g. various pain medications); please refer to the manufacturer's label for risks associated with taking any medication.

7.1.6 Risk Management Procedures

The most important risk management procedures will be thorough subject training, meticulous A-Tube implantation procedures, and careful medical monitoring. Physicians who will perform A-Tube placement will follow the procedures outlined in the AspireAssist A-Tube™ Instructions for Use (IFU).

The inclusion and exclusion criteria and careful initial medical evaluation will help exclude potential participants who are at high risk for procedure and treatment related complications. The careful medical monitoring protocol ensures that participants are closely followed and that potential complications can be identified early and managed appropriately. Subjects will be carefully monitored by the medical staff associated with the study for the duration of the study.

7.2 Safety Criteria

All participants will be carefully monitored by a physician and research coordinator during this study. Safety will be monitored by:

- 1. Incidence of device-, procedure- and therapy- related adverse events
- 2. Incidence of device-related or unrelated serious adverse events, including unanticipated adverse device effects

7.3 Adverse Event Reporting

All adverse events must be logged on the Case Report Forms (please see **Appendix K** for **Adverse Events Guidelines**). There are special procedures for handling serious adverse events and unanticipated adverse events as described and defined in this section.

7.3.1 Adverse events (AE)

The definitions of an Adverse Event and a treatment-emergent adverse event are as follows:

Adverse event (AE): any untoward, noxious, or unintended event experienced by a subject in a clinical trial of an investigational device, whether considered related to that investigational device or not. This definition also encompasses: 1) events that result from abuse of the device, 2) symptoms reported by the subject, 3) signs detected by the investigator or other competent observer, and 4) medically important deviations from normalcy in the results of ancillary investigations.

Treatment-emergent adverse event: an AE that is new in onset or aggravated in severity or frequency following placement of the investigational

device. This includes any change from baseline physical examination findings or results of diagnostic procedures (e.g., laboratory test, ECG, X-ray) that is clinically significant, i.e., requires diagnostic or therapeutic intervention beyond confirmation alone; however, such a finding shall not be recorded as a separate AE if it is intrinsic to, or results in, a clinical diagnosis that is recorded as an AE.

a. Anticipated Adverse Device Effects

The following events have been identified as possible (anticipated) adverse events that could be related to A-Tube implantation and use:

- 1) Risks of endoscopic placement of the A-Tube, as outlined in Section 7.1.1, are examples of procedure-related adverse events.
- 2) Risks related to the presence of the A-Tube, as outlined in Section 7.1.2, are examples of device-related adverse events.
- 3) Risks of Aspiration Therapy, as outlined in Section 7.1.3, are examples of therapy-related adverse events.
- 4) Behavioral Risks, as outlined in Section 7.1.4, are examples of therapy-related adverse events.
- 5) Risks related to concomitant drug therapy, as outlined in Section 7.1.5, are examples of study-related concomitant medication-related adverse events.
- 6) Risks of weight loss include gallstone formation, bone demineralization, alopecia, dehydration, changes in bowel habits, and loose skin are examples of therapy-related adverse events.

If the subject is female, the procedure may involve unforeseeable risks to an embryo or fetus should the subject become pregnant.

Anticipated adverse events that are NOT deemed serious adverse events need only be recorded on the CRF.

b. Unanticipated Adverse Device Effects

Unanticipated adverse device effects (UADE) are defined as "any *serious* adverse effect on health or safety or any life-threatening problem or death caused by, or associated with, a device, if that effect, problem, or death was not previously identified in nature, severity, or degree of incidence in the investigational plan or application (including a supplementary plan or application), or any other unanticipated *serious* problem associated with a device that relates to the rights, safety, or welfare of subjects'

All unanticipated adverse events and deaths must be reported by telephone and in writing immediately, or within 48 hours of knowledge of the event, to Aspire Bariatrics. The PI must also inform the relevant Institutional Review Board, Medical Ethics Committee or similar body, if applicable, per local regulations.

The telephone report must be followed by a written report that is emailed or faxed to the Sponsor within two days to include the date of occurrence, complete description of the event, severity, duration (when appropriate), action taken, outcome, and the investigator's assessment of relatedness to the endoscopic procedure or the presence of the A-Tube. The incident shall also be recorded in the CRF on the Adverse Event Form.

c. Serious Adverse Event (SAE)

Serious adverse event (SAE): any AE that is fatal, immediately lifethreatening (i.e., presents an immediate risk of death at the time of the AE, not an AE that hypothetically might have caused death if it were more severe), requires inpatient hospitalization for more than 24 hours, causes permanent or significant disability, requires medical or surgical intervention to prevent permanent sequelae, or any of the outcomes listed above.

When the investigator or designee becomes aware that a serious AE has occurred, the Sponsor or designee must be notified immediately by telephone and followed by an e-mailed or faxed written report, regardless of the relationship (or lack thereof) of the AE to the study treatment. The investigator will be notified of the occurrence of serious, unexpected AEs at other study sites. If such AEs are also associated with the use of the study device (i.e., there is a reasonable possibility that the AE may have been caused by the device) and are thus deemed significant new adverse effects or

risks with respect to the investigational device, the investigator must promptly inform the relevant Institutional Review Board.

Information regarding SAEs occurring at any site will be disseminated by the Sponsor to all study sites and the information reported to the Ethical Committee as required by local regulations.

The names and telephone numbers of the individuals who shall be contacted regarding safety issues are listed in **Appendix L** ("**Sponsor Contact Information**") of this protocol.

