2.3 Safety Outcomes

Safety will be evaluated by:

- 1. Incidence of device-related, procedure-related and therapy- related adverse events
- 2. Incidence of device-related or unrelated serious adverse events, including unanticipated adverse device effects
- 3. Development of adverse eating behaviors as measured by EDE and QEWP-R

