After endoscopic A-Tube placement is completed, subjects are observed in the recovery area of the endoscopy suite or admitted to the hospital for up to 24 h, at the discretion of the physician performing the procedure.

Antibiotic prophylaxis for 24 hours is given to each subject: 1 g of cefazolin sodium intravenously approximately 30-60 minutes before A-Tube placement and subsequent oral cephalexin (500 mg q 12 hrs) for 24 hours (two doses) after endoscopy. If the subject is allergic to cefazolin, either clindamycin (900 mg intravenously) can be given followed by oral clindamycin therapy (300 mg p.o. every 8 hours) for 24 hours (three doses) after endoscopy or vancomycin (1 gram intravenously) can be given before the procedure (no post endoscopy therapy. Ultimately, the exact antibiotic regimen used in any subject is at the discretion of the study site gastroenterologist.

If the A-Tube cannot be placed safely, based on the judgment of the endoscopist, or if an exclusion criteria is discovered during endoscopy, the procedure should be terminated and subject discharged from further participation in the study.

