5.6 Withdrawal Criteria

Subjects are informed orally and in writing that they are free to withdraw from the study at any time without bias or prejudice. Subjects should be encouraged to complete the next scheduled study visit prior to withdrawal (an unscheduled visit may also be performed).

A subject who decides to stop all therapeutic interventions will have the A-Tube removed and will be followed by the study site physician until the stoma has healed, returning for three bi-monthly visits over a 6-month period.

If a subject decides to withdraw completely from the study, he/she may do so at any time. The reason for discontinuation must be recorded in the source documentation and on the Study Exit CRF. Possible reasons for premature discontinuation may include but are not limited to the following:

- Withdrawal of consent: Subject decides to withdraw from the study.
- Adverse Events: Subjects must be followed until the adverse experience resolves or until a stable clinical end-point is reached.
- Lost to follow-up: A letter will be sent to the subject when three attempts to reach the subject by telephone and/or email have failed. The subject will be considered lost to follow-up if he/she is not able to be reached within 4 months after failure to return for follow-up visits.

The Sponsor can terminate a subject's involvement in this study prior to completion for ethical or safety reasons at any time. If, at any time during the

study, a subject begins taking a weight loss medication or supplement, the subject should be withdrawn from the study.

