7.3.2 Duration of Follow-up after Adverse Event

All treatment-emergent AEs must be followed until resolution or until a stable clinical end-point is reached. All measures required for AE management and the ultimate outcome of the AE must be recorded in the source documents and reported to Aspire Bariatrics.

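### Subjects whose A-Tube placement is abandoned leave the study with no safety follow-up that clearly reaches them, so delayed procedure-related events can be missed

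*Protocol*

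**What the plan says.** - **Abandoned placement (Protocol 5.4.1).** If the endoscopist judges that the tube cannot be placed safely, or finds an exclusion criterion during endoscopy, "the procedure should be terminated and subject discharged from further participation in the study". The section sets no later safety contact and gives no timing for the discharge.
- **Treatment-emergent event (7.3.1).** An event that is "new in onset or aggravated in severity or frequency following placement of the investigational" device. There is no start point for an attempt that places no tube, or for Control.
- **Duty to follow (7.3.2).** "All treatment-emergent AEs must be followed until resolution or until a stable clinical end-point is reached".
- **Withdrawal (5.6).** Among the reasons for discontinuation: "Adverse Events: Subjects must be followed until the adverse experience resolves or until a stable clinical end-point is reached". This is not limited to one arm.
- **Safety outcome (2.3).** The first item is "Incidence of device-related, procedure-related and therapy- related adverse events". Section 7.3.1 classes the endoscopic risks listed in 7.1.1 as procedure-related.
- **Recording.** An adverse event is any untoward event "experienced by a subject in a clinical trial of an investigational device, whether considered related to that investigational device or not" (7.3.1). Section 7.3 adds "All adverse events must be logged on the Case Report Forms". Serious events go to the sponsor "regardless of the relationship (or lack thereof) of the AE to the study treatment" (7.3.1).
- **Analysis.** Section 8.4 tabulates adverse events in both arms. Section 8.5 runs the safety analyses on an ITT population made up of subjects who received treatment. Section 2.2(viii) counts procedural success over everyone who has the endoscopy.

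**The concern.** A subject whose placement is abandoned may already have had sedation, upper endoscopy and, depending on when the attempt stops, a skin incision and gastric puncture. Section 7.1.1 lists bleeding, infection, aspiration pneumonia and perforation among the risks, and some of these can show themselves after the subject has gone home. The logging and reporting rules work only if the site hears of the event: the duty to notify a serious event starts when the investigator learns of it. A subject who is out of the study and has no scheduled contact may never report a delayed complication.

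At stake is a named safety outcome of a pivotal premarket device trial. The protocol counts these subjects when it asks whether the tube could be placed. It does not clearly count them when it asks what harm the attempt did.

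**Working it through.** **Which follow-up rule reaches an abandoned placement?**

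| Rule | Runs from | Reaches a subject with no tube? |
|---|---|---|
| Day 1 call (5.4.2.1) | the day after tube placement | Not clearly |
| Day 7 visit (5.4.2.2) | the insertion procedure; includes stoma healing | Not clearly: 5.4.1 has already ended participation |
| Follow-up to resolution (7.3.2) | treatment-emergent events only, so after device placement (7.3.1) | No, read literally |
| Withdrawal (5.6) | exit because of an adverse event | Only if that is the recorded reason; not clearly if the reason is inability to place the tube |
| Six-month follow-up (5.8) | explantation | No: nothing was implanted |
| Safety population (8.5) | having undergone treatment | Unclear: 5.4.2.3 starts Aspiration Therapy when the Skin-Port is fastened |

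**Size.** The protocol gives no figure for this gap, so there is none to reproduce. The inputs are 117 AT subjects (8.1.1), PEG placement success of 95% to 98% and PEG complication rates of 4.9% to 10.8% (both 1.3.1). Applying general PEG figures to the A-Tube, and the overall complication rate to abandoned attempts, are assumptions.

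1. Expected failed placements = 117 × (1 − success rate): 117 × 0.02 = 2.3, and 117 × 0.05 = 5.9.
2. Chance of at least one = 1 − (success rate)^117: 91% at 98% success, 99.8% at 95%.
3. Expected complications among them: 2.34 × 0.049 = 0.11, and 5.85 × 0.108 = 0.63.
4. Expected complications over all 117: 117 × 0.049 = 5.7, and 117 × 0.108 = 12.6.
5. Share lost if every one were missed: 0.115 / 5.73 = 2%, and 0.632 / 12.64 = 5%. With a common complication rate this share equals the failure rate.
6. Effect on the reported rate if these subjects stay in the denominator and their events are missed: (5.73 − 0.115) / 117 = 4.8% instead of 4.9%, and (12.64 − 0.632) / 117 = 10.3% instead of 10.8%. If they are dropped from both numerator and denominator, the rate does not shift under the equal-risk assumption, but it no longer describes everyone exposed to the procedure.

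Exclusions found at endoscopy would add to the number discharged; the protocol gives no rate for them.

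**Control.** No Control subject receives a device, so no Control event meets the 7.3.1 definition and 7.3.2 sets no duty for them. Control events are nevertheless assessed at 14 visits from Week 0 to Week 52 (5.3), logged (7.3) and tabulated (8.4). What remains is an event still open when a Control subject completes Week 52.

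**The case against.** The best counter-argument is that the treatment-emergent wording drives almost nothing. The safety outcomes and the between-arm test refer to adverse events, not treatment-emergent ones; all events are to be logged and all serious events reported. This stands. Changing the definition alone would alter no reported rate, and a complication known when the subject leaves must be recorded. It does not help with a complication that appears later in someone no longer seen.

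The procedure may also be abandoned early. In 5.4.1 the diagnostic endoscopy and the choice of site by transillumination and finger indentation come before incision and puncture, so abandoned attempts may carry less risk than completed ones. A reader might infer the opposite, that failed attempts are where complications concentrate; the protocol gives no support for that.

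The feasibility trial placed the tube in 11 of 11 subjects (1.3.3 results). That is reassuring but weak: at 95% success, 11 of 11 has probability 0.95^11 = 57%.

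Finally, the adverse event guidelines (Appendix K) and the A-Tube instructions (Appendix D) are not available here and may set out follow-up after an abandoned attempt. Even so, the protocol body should agree with them.

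**Conclusion.** The gap is real but small. As written, no rule clearly keeps an abandoned-placement subject under safety observation or in the procedure-related denominator. On the protocol's PEG figures this concerns about 2 to 6 of 117 AT subjects and 0.1 to 0.6 expected complications, at most 2% to 5% of procedure-related events and about half a percentage point on the rate. These figures assume that PEG rates carry over to the A-Tube and that abandoned attempts carry the average risk; the loss is smaller if some of the events are known at exit.

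Three stronger readings are not supported:

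- **That all Control events escape follow-up, or that the comparison of arms is biased.** Section 5.6 follows exits due to an adverse event in either arm, and 8.4 counts subjects with at least one event, a count that does not depend on whether the event resolves. The Control gap is limited to 7.3.2 setting no duty for an event still open at study end.
- **That a large share of procedure-related events would be lost.** Missing two events would be 2 / 12.6 = 16% to 2 / 5.7 = 35% of the total, but only 0.1 to 0.6 are expected in this group. Treating the count as Poisson with mean 0.63, the chance of two or more is about 13%; with mean 0.11 it is under 1%.
- **That subjects are discharged immediately.** Section 5.4.1 gives no timing.

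**What to change.** Reconcile Protocol 5.4.1, 5.6, 7.3.1, 7.3.2 and 8.5:

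1. **5.4.1.** State that a subject with an attempted but abandoned placement receives no device therapy, as now, but stays in the study for safety observation through the post-procedure contacts already in Table 1 (Day 1 call, Day 7 visit) and until any adverse event resolves or stabilises. Align 5.6 with this.
2. **7.3.1 and 7.3.2.** Word the follow-up duty to cover adverse events from the start of the procedure in the AT arm, whether or not a tube is placed, and from Week 0 in Control, including events still open at study end.
3. **8.5.** State that the denominator for procedure-related events is every subject undergoing endoscopy, matching 2.2(viii).

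The cost is a few sentences, plus one call and one visit for roughly 2 to 6 subjects on the assumptions above, and any longer follow-up of events that remain open. The downside for the sponsor is a procedure-related event rate that may be slightly less favourable.

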7.3.2 Duration of Follow-up after Adverse Event

All treatment-emergent AEs must be followed until resolution or until a stable clinical end-point is reached. All measures required for AE management and the ultimate outcome of the AE must be recorded in the source documents and reported to Aspire Bariatrics.

7.3.3 Definitions for the Grades of Severity of Adverse Event

1) Minimal: Awareness of sign or symptom, but easily tolerated

2) Mild: tolerated w/ some difficulty

3) *Moderate*: interference with some normal daily activities4) *Significant*: inability to perform normal daily activities

5) Severe: requires hospitalization

